11. Current or previous other malignancy within 3 years of study entry, except cured basal or squamous cell skin cancer, superficial bladder cancer, prostate intraepithelial neoplasm, carcinoma *in situ* of the cervix, or other noninvasive or indolent malignancy without sponsor approval.
12. History of stroke or intracranial hemorrhage within 6 months of the date of study drug administration.
13. Chronic or current active infectious disease requiring systemic antibiotics, antifungal, or antiviral treatment, and exposure to a live vaccine within 30 days of study drug administration.
14. Known human immunodeficiency virus (HIV) infection or positivity on immunoassay.  
Note: HIV screening test is optional for subjects enrolled in the United States, but subjects with known HIV infection enrolled in the United States will be excluded.
15. Liver disease:
  - a. Evidence of hepatitis B virus (HBV) or hepatitis C virus (HCV) infection or risk of reactivation: HBV DNA and HCV RNA must be undetectable. Subjects cannot be positive for hepatitis B surface antigen (HBsAg) or anti-hepatitis B core antibody. Subjects who have positive anti-HBs as the only evidence of prior exposure may participate in the study provided that there is both 1) no known history of HBV infection, and 2) verified receipt of hepatitis B vaccine.
16. Clinically significant cardiac disease, including unstable angina, acute myocardial infarction, and or cardiac conduction issues within 6 months of the date of study drug administration.

17. Current New York Heart Association Class II to IV congestive heart failure or uncontrolled arrhythmia.
18. Presence of an abnormal ECG that is clinically meaningful. Screening QTc interval > 450 milliseconds is excluded (corrected by Fridericia). In the event that a single QTc is > 450 milliseconds, the subject may enroll if the average QTc for 3 ECGs is < 450 milliseconds.
19. Unable to swallow oral medication, malabsorption syndrome, disease significantly affecting gastrointestinal function, total resection of the stomach or small bowel, ulcerative colitis, symptomatic inflammatory bowel disease, or partial or complete bowel obstruction.
20. Known hypersensitivity or severe reaction to INCB050465 or its excipients (INCB050465 IB).
21. Currently pregnant or breastfeeding.

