**Table 4: Schedule of Assessments**

**Note: Upon implementation of Protocol Amendment 4, only the schedules of assessments in Table 6 and Table 7 should be followed.**

Procedure	Section	Screening	Treatment				EOT	Safety Follow-Up	Disease Follow-Up	Survival Follow-Up
		Day -28 to -1	Day 1	Day 15 (± 3 Days)	Every 3 Weeks (± 3 Days)	Every 12 Weeks (± 3 Days)		EOT + 30-35 Days		Every 12 Weeks (± 1 Week)
Informed consent	7.1	X								
Contact IWRS	7.2	X	X		X		X			
Inclusion & exclusion criteria	3.1 3.2	X	X							
Demography and medical history	7.3.1	X								
Prior/concomitant medications	7.3.1.1	X	X	X	X		X	X		
Comprehensive physical exam	7.4.2	X a					X			
Disease-specific physical exam	7.4.2.1		X	X	X			X		
Vital signs	7.4.3	X	X	X	X		X	X		
12-lead ECG	7.4.4	X	X	X		X	X	X		
ECOG status	7.5.6	X	X		X		X	X		
AE assessment	7.4.1	X	X	X	X		X	X		
FDG-PET/CT scan	7.5.1 7.5.2	X	Every 9 weeks (± 1 week) through Week 27, then every 18 weeks (± 1 week) thereafter. b							
Bone marrow exam	7.5.3	X c								
Study drug dispensing	5.1		X		X d					
Study drug accountability	5.3		X		X		X			
INCB050465 administration	5.2.1		X	X	X					
Disease follow-up	6.4.2								X e	
Survival follow-up	6.4.3									X f

FDG = fluorodeoxyglucose; PET = positron emission tomography.

a Height required at screening only.

b If the PET-CT is of diagnostic quality, then a separate CT does not need to be performed. If CT is not available, is not practicable, or is contraindicated, then an MRI may be substituted. Every effort must be made to use the same modality for disease assessment throughout the study for each individual subject.

c Required at baseline except for reasons provided in Section 7.5.3. Also required if needed to confirm CR/CMR.

d Study drug will be dispensed at Weeks 1, 4, 7, and 10, and every 12 weeks thereafter.

e Only for subjects who discontinue study treatment for reasons other than disease progression.

f May be conducted by phone or email.

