### **7.4.4. Twelve-lead Electrocardiograms**

All 12-lead ECGs will be performed with the subject in a recumbent or semirecumbent position after 5 minutes of rest. Baseline ECGs will be obtained during screening using a single measurement, but can be done in triplicate if the single QTc measurement is > 450 milliseconds (corrected by Fridericia; see Section 3.2). Electrocardiograms will also be obtained during the Day 1 visit (triplicate measurements) before the subject receives the first dose of study drug. Triplicate ECGs will be performed predose and 1.5 hours ( $\pm$  15 minutes) after receiving INCB050465 on Day 15. When triplicate ECGs are being obtained, individual measurements should be performed 5 minutes ( $\pm$  3 minutes) apart. All 12-lead ECGs obtained at subsequent timepoints (single measurements) will be compared with the baseline 12-lead ECGs as follows:

- For ECG morphology, all postdose ECG recordings will be compared with Day 1 predose ECGs.
- For the calculation of changes in cardiac intervals (eg, QT interval), the intervals from the screening and Day 1 predose (triplicate) ECGs will be computed and averaged and used as the baseline for comparison of all postdose intervals.

If a single measurement demonstrates a QTc interval > 500 milliseconds, 2 more ECGs should be obtained over a brief period, and the averaged QTc intervals should be used to determine whether the study treatment should be interrupted.

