**9.4.2.4. Electrocardiograms**

Descriptive statistics and mean change from baseline will be summarized for the ECG parameter at each assessment time. Average of all values before the first dose of study drug will be used as the baseline value. Criteria for clinically notable ECG abnormalities are defined (see Table 13). The abnormal values for subjects exhibiting clinically notable ECG abnormalities will be listed. Alert ECG values are defined as an absolute value outside the defined range and absolute percentage change > 25% (30% for QRS) interval. The abnormal values for subjects exhibiting alert ECG abnormalities will be listed. Outliers of QT, QTcB, and QTcF, defined as absolute values > 450 milliseconds or change from baseline > 30 milliseconds, will also be listed.

[figure not shown]

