8.5. Electrocardiograms

Twelve-lead ECGs including PR, QRS, QT, QTcF, and RR intervals will be obtained for each subject during the study. Values at each scheduled visit, change, and percentage change from baseline will be summarized for each ECG parameter. Baseline will be determined as the average of all nonmissing values before the first administration of INCB050465.

Normal ranges for ECG values are defined in Table 3. Electrocardiogram values will be considered abnormal as well if the absolute percentage change from baseline is more than 25% (30% for QRS interval). Subjects exhibiting ECG values outside the normal ranges will be listed with study visit and assigned treatment group. Abnormal values for subjects with alert ECG values, defined as both the absolute value and the percentage change from baseline being outside normal ranges, will be identified and listed. Outliers of QT and QTcF values, defined as absolute values > 450 msec or change from baseline > 30 msec, will be summarized.

Table 3: Normal Ranges for Electrocardiogram Values

Parameter	High Threshold	Low Threshold
QTcF	> 460 msec	< 295 msec
PR	> 220 msec	< 75 msec
QRS	> 120 msec	< 50 msec
QT	> 500 msec	< 300 msec
RR	> 1330 msec	< 600 msec

QTcF = Fridericia's correction.

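### SAP 8.5 applies one outlier rule (>450 ms or change >30 ms) to both uncorrected QT and QTcF. It disagrees with Table 3 in the same section and lets heart rate alone create QT outliers.

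*SAP*

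**What the plan says.** **Outlier rule.** SAP 8.5: "Outliers of QT and QTcF values, defined as absolute values > 450 msec or change from baseline > 30 msec, will be summarized". The result is Table 3.5.6, marked for in-text use in SAP Appendix A. Protocol 9.4.2.4 uses the same limits ("defined as absolute values > 450 milliseconds or change from baseline > 30 milliseconds") but also covers QTcB and plans only a listing. SAP 10.1 records no changes to protocol-defined analyses.

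**Normal ranges.** SAP Table 3, in the same section, has upper limits of 500 ms for QT, 460 ms for QTcF and 1330 ms for RR. A value is also abnormal if it changes from baseline by more than 25% (30% for QRS).

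**Entry limit.** Exclusion criterion 18 (Protocol 3.2) excludes a screening QTcF above 450 ms. After one high reading, however, "the subject may enroll if the average QTc for 3 ECGs is < 450 milliseconds".

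**Readings.** On Day 15, "Triplicate ECGs will be performed predose and 1.5 hours" after dosing (Protocol 7.4.4). After that: "All 12-lead ECGs obtained at subsequent timepoints (single measurements) will be compared with the baseline 12-lead ECGs as follows". Protocol Table 4 schedules these every 12 weeks, at end of treatment and at safety follow-up. For baseline, SAP 8.5 says: "Baseline will be determined as the average of all nonmissing values before the first administration of INCB050465". It does not say whether the outlier rule applies to each reading or to the visit mean.

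**The concern.** Two sets of limits for the same intervals stand side by side in one section, with no reason given for the difference. One of the two intervals in the outlier rule is not corrected for heart rate, so the rule can count a slower pulse as a QT finding. The rule does not require the value to be new relative to baseline. Its absolute limit equals the QTcF entry limit, so a subject admitted just below 450 ms needs only a small upward variation to be counted.

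The trial has a single treatment regimen and no control arm, so nothing in it shows how many such flags would occur without the drug. A reader of Table 3.5.6 would have to interpret the count against an unknown background.

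**Working it through.** Neither document states an expected outlier rate, so there is no figure to reproduce. Steps 1 to 3 use document limits and arithmetic only, at illustrative QTcF and heart-rate values. Step 4 needs variability figures that the documents do not give.

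**1. The limits side by side**

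| Interval | Outlier rule | Table 3 upper limit | Inside Table 3 but an outlier |
|---|---|---|---|
| QT | >450 ms | >500 ms | above 450, up to 500 ms |
| QTcF | >450 ms | >460 ms | above 450, up to 460 ms |

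A QT of 470 ms and a QTcF of 455 ms both fall in the last column.

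**2. Heart rate and the change criterion**

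Fridericia: QT = QTcF × RR^(1/3), with RR in seconds = 60 / heart rate. Hold QTcF at 415 ms.

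- 85 bpm: RR = 0.706 s, QT = 369.5 ms.
- 65 bpm: RR = 0.923 s, QT = 404.1 ms.
- Change: 404.1 − 369.5 = +34.6 ms, above 30 ms.

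As a percentage this is 34.6 / 369.5 = 9.4%, well under the 25% criterion. Both RR values lie inside Table 3's 600 to 1330 ms. A fall from 80 to about 63.6 bpm is already enough for +30 ms.

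**3. Heart rate and the absolute criterion**

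At Table 3's RR limit of 1330 ms, RR^(1/3) = 1.0997.

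- QT exceeds 450 ms once QTcF exceeds 450 / 1.0997 = 409 ms.
- A QTcF of 450 ms gives QT = 450 × 1.0997 = 495 ms, still inside the 500 ms limit.

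At a QTcF of 430 ms, QT exceeds 450 ms when heart rate falls below about 52 bpm. The QT part of the rule can therefore fire while QT, QTcF and RR are all inside Table 3.

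**4. Share of subjects flagged with no drug effect (assumed inputs)**

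Both simulations use 200,000 subjects per scenario, apply the entry rule and take baseline as the average of the screening ECG and the Day 1 triplicate. Any postbaseline flag counts.

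*Simulation 1.* True QTcF mean 415 ms, SD 18; heart rate mean 78 bpm, SD 11. Cases are labelled by within-subject QTcF SD, within-subject heart-rate SD and number of postbaseline visits.

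| Case | QTcF flag | QT flag | Either |
|---|---|---|---|
| 8 ms, 6 bpm, 3 visits | 5.0% | 10.0% | 13.8% |
| 10 ms, 8 bpm, 4 visits | 9.6% | 24.9% | 30.2% |
| 12 ms, 8 bpm, 6 visits | 20.0% | 35.9% | 44.6% |

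*Simulation 2.* QTcF mean 405 to 425 ms, between-subject SD 15 to 20, within-subject SD 6 to 15; heart rate mean 75 bpm, SD 10 between and 8 within subjects. Day 15 enters as triplicate means at two times, followed by 3 or 5 single ECGs. (About 9 months of treatment with ECGs every 12 weeks gives about 3, plus end of treatment and safety follow-up, so 5.)

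| Criterion | Range flagged |
|---|---|
| QTcF >450 ms | 0.5% to 34% |
| QTcF change >30 ms | 0% to 21.5% |
| QTcF, either criterion | 0.5% to 44% |
| QT >450 ms | 4% to 18% |
| QT change >30 ms | 22% to 45% |
| Any QT or QTcF flag | 24% to 65% |
| For comparison: QTcF >460 ms | 0.0% to 17% |
| For comparison: QT >500 ms | 0.0% to 1.0% |

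With QTcF mean 415, SD 18 between and 10 within subjects, and 4 single ECGs, varying only the heart-rate assumptions moves QT change >30 ms between 17% and 47%, and any flag between 29% and 53%.

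Over both simulations, any flag runs from about 14% to 65%. In the second, the change criterion on uncorrected QT is the main driver.

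**The case against.** The case for leaving the rule alone has five parts.

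- **The flag rate is not a document fact.** This stands. A reader might take a range such as 14% to 45% as the rate this trial will produce. It follows from assumed means and SDs, and other plausible values move it widely, so it is illustrative only. Groups A and B are also reported separately, so a count out of 120 would match no planned output.
- **The rule may not work on single ECGs.** This stands in part. Later ECGs are single, but Day 15 is triplicate and the SAP is silent on reading versus mean. That is a gap to close, not a stated single-reading rule.
- **The table may already separate the criteria.** This is possible. Table 3.5.6 is a standard table whose shell is not in the documents. The SAP text does not require separate rows, so they cannot be relied on.
- **A QTcF signal would still show.** This stands. A reader might infer that the rule hides a real QTcF effect. SAP 8.5 also summarizes QTcF value and change by visit (Table 3.5.5), and Listings 2.10.1 to 2.10.3 give all, abnormal and alert ECG values.
- **Using the entry limit as the screen is reasonable.** Largely so. Most postbaseline QTcF values above 450 ms will be new relative to an eligible baseline. The missing condition matters mainly for subjects close to the limit, and it has no such defence for uncorrected QT, which has no entry limit.

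None of this answers the mismatch with Table 3 or the use of uncorrected QT.

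**Conclusion.** The concern holds as an unreconciled pair of limits and a poor choice of variable for one of them. Steps 1 to 3 need no variability assumption: a QT from just above 450 to 500 ms, or a QTcF from just above 450 to 460 ms, is classified both ways, and heart rate alone can produce a QT outlier.

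The size in subjects is not derivable from the documents. Roughly 14% to 65% for any flag without drug effect is conditional on the stated assumptions. For QTcF alone the two simulations together give 0.5% to 44%, so removing QT lowers the background but need not remove it.

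The consequence is limited to the counts in one descriptive in-text table. A reader might also infer that the rule affects dosing. The documents do not support that: Protocol 7.4.4 ties the interruption decision to the averaged QTc after a single value above 500 ms. The change is still worth making, because the trial has no background rate against which to read the count.

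**What to change.** In SAP 8.5 and Table 3.5.6:

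1. Base the outlier summary on QTcF and drop uncorrected QT, or use Table 3's 500 ms as the QT limit.
2. Reconcile the QTcF limits of 450 and 460 ms, or state why the two displays differ.
3. Report the absolute and change criteria in separate rows, and add a QTcF >500 ms row to match the repeat-ECG level in Protocol 7.4.4.
4. Count only values new versus baseline: above the limit after baseline, and not above it at baseline.
5. Use the visit mean where triplicates are taken (Day 15), and say so.

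While editing, record in SAP 10.1 that the protocol's QTcB outliers were dropped, with the reason. No cut-offs from outside the documents are needed.

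The cost is SAP wording and a few table rows, programmed from data already collected. The downside is that one any-outlier count becomes several smaller counts, which takes slightly more space and gives no single headline figure.

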9. INTERIM ANALYSES

9.1. Overview of Interim Analyses

An interim futility analysis is planned when the first 40 subjects in Group A have been treated and have been evaluated for response or have permanently discontinued study treatment because of disease progression, withdrawal of consent, or death. Group A of the study will be terminated for futility if ≤ 13 of the 40 subjects have responded (ie, CR/CMR or PR/PMR) based on assessments provided by the IRC; otherwise the study will continue. A timely assessment of response will be performed to avoid the risk of overenrollment.

An IDMC will be charged with evaluating interim futility results. The IDMC will consist of clinicians and an independent statistician. The IDMC will make recommendations to the sponsor at the planned interim futility analysis in Group A. The process by which the IDMC will make recommendations and decisions will be documented in the IDMC charter. Additional operational details of the interim analyses, including tables, figures, and listings provided to the DMC, will be provided in the DMC Charter.

9.2. Derivations and Calculations for Interim Analyses

The futility analysis will be conducted for exactly 40 subjects with stopping boundary as stated in Section 9.1. There is no efficacy interim analysis planned for the study.

10. CHANGES AND MODIFICATIONS TO THE ANALYSIS PLAN

All versions of the SAP are listed in Table 4.

Table 4: Statistical Analysis Plan Versions

SAP Version	Date
Original	22 MAR 2018

10.1. Changes to Protocol-Defined Analyses

Not applicable.

10.2. Changes to the Statistical Analysis Plan

Not applicable.

APPENDIX A. PLANNED TABLES AND FIGURES

This appendix provides a list of the planned tables and figures for the Clinical Study Report for Group A and Group B, unless otherwise specified. Outputs from Group A will have ".1" at the end of the numbering. Outputs from Group B will have ".2" at the end of the numbering. Standard tables will follow the conventions in the Standard Safety Tables initial version. Shells are provided for nonstandard tables. In-text tables are identical in structure and content as appendix tables, but follow a Rich Text Format.

The list of tables, figures, and the shells are to be used as guideline. Modifications of the list or shells that do not otherwise affect the nature of the analysis will not warrant an amendment to the SAP.

Tables

Table No.	Title	Population	Standard	In-Text
Baseline ar	nd Demographic Characteristics			
1.1.1	Analysis Populations	FAS	X	X
1.1.2	Summary of Subject Disposition	FAS	X	X
1.1.3	Summary of Number of Subjects Enrolled by Country and Site	FAS	X	
1.2.1	Summary of Demographics and Baseline Disease Characteristics	FAS		X
1.3.1	Summary of Disease History	FAS		X
1.3.2	Summary of Prior Cancer Therapy	FAS		
1.3.3	Summary of Prior Systematic Cancer Therapy by WHO Drug Class and Preferred Term	FAS	X	
1.4.1	Summary of Prior Medications	FAS	X	
1.4.2	Summary of Concomitant Medications	FAS	X	
1.5.1	Summary of General Medical History	FAS	X	
Efficacy				
2.1.1	Summary of Best Overall Response and Overall Response Rate as Determined by IRC	FAS		X
2.1.2	Summary of Best Overall Response and Overall Response Rate as Reported by Investigator (Group A only)	FAS		X
2.1.3	Summary of Best Overall Response and Overall Response Rate as Determined by IRC by Subgroup (Group A only)	FAS		X
2.2.1	Summary of Duration of Response as Determined by IRC	FAS		X
2.2.2	Summary of Duration of Response as Reported by Investigator (Group A only)	FAS		X
2.2.3	Summary of Progression-Free Survival as Determined by IRC	FAS		X
2.2.4	Summary of Progression-Free Survival as Reported by Investigator (Group A only)	FAS		X
2.2.5	Summary of Overall Survival	FAS		X
2.2.6	Summary of Best Change in Target Lesion Size as Determined by IRC	FAS		X
2.2.7	Summary of Best Change in Target Lesion Size as Reported by Investigator	FAS		X

Table No.	Title	Population	Standard	In-Text
Safety				
3.1	Summary of Exposure and Compliance	Safety		X
3.2.1	Overall Summary of Treatment-Emergent Adverse Events	Safety	X	X
3.2.2	Summary of Treatment-Emergent Adverse Events by MedDRA System Organ Class and Preferred Term	Safety	X	X
3.2.3	Summary of Treatment-Emergent Adverse Events by MedDRA Preferred Term in Decreasing Order of Frequency			X
3.2.4	Summary of Treatment-Emergent Adverse Events by MedDRA System Organ Class, Preferred Term, and Maximum Severity	Safety X		
3.2.5	Summary of Grade 3 or 4 Treatment-Emergent Adverse Events by MedDRA System Organ Class and Preferred Term	Safety	Safety X X	
3.2.6	Summary of INCB050465 Treatment-Related Adverse Events by MedDRA System Organ Class and Preferred Term	Safety	X	
3.2.7	Summary of INCB050465 Treatment-Related Adverse Events by MedDRA System Organ Class, Preferred Term, and Maximum Severity	Safety	X	
3.2.8	Summary of Grade 3 or 4 INCB050465 Treatment-Related Adverse Events by MedDRA System Organ Class and Preferred Term	Safety	X	
3.2.9	Summary of Treatment-Emergent Adverse Events With a Fatal Outcome by MedDRA System Organ Class and Preferred Term	Safety	X	X
3.2.10	Summary of Serious Treatment-Emergent Adverse Events by MedDRA System Organ Class and Preferred Term	Safety	X	X
3.2.11	Summary of Serious Treatment-Emergent Adverse Events by Preferred Term in Decreasing Order of Frequency	Safety	X	X
3.2.12	Summary of INCB050465 Treatment-Related Serious Adverse Events by MedDRA System Organ Class and Preferred Term	Safety	X	X
3.2.13	Summary of Treatment-Emergent Adverse Events Leading to INCB050465 Dose Reduction by MedDRA System Organ Class and Preferred Term	Safety	X	
3.2.14	Summary of Treatment-Emergent Adverse Events Leading to INCB050465 Dose Interruption by MedDRA System Organ Class and Preferred Term	Safety	X	
3.2.15	Summary of Treatment-Emergent Adverse Events Leading to Discontinuation of INCB050465 by MedDRA System Organ Class and Preferred Term	Safety	X	X
3.2.16	Summary of Selected Treatment-Emergent Adverse Events of Special Interest by Highest Grade	Safety		X
3.2.17	Summary of Time to Onset of Selected Treatment-Emergent Adverse Events of Special Interest	Safety		X
3.2.18	Summary of Treatment-Emergent Adverse Events During QW Schedule by MedDRA System Organ Class and Preferred Term	Safety	X	X

Table No.	Title	Population	Standard	In-Text
3.2.19	Summary of Grade 3 or 4 Treatment-Emergent Adverse Events During QW Schedule by MedDRA System Organ Class and Preferred Term	Safety	X	X
3.2.20	Summary of INCB050465 Treatment-Related Adverse Events During QW Schedule by MedDRA System Organ Class and Preferred Term	Safety	X	
3.2.21	Summary of Treatment-Emergent Adverse Events With a Fatal Outcome During QW Schedule by MedDRA System Organ Class and Preferred Term	Safety X		X
3.2.22	Summary of Serious Treatment-Emergent Adverse Events During QW Schedule by MedDRA System Organ Class and Preferred Term	Safety	Safety X	
3.2.23	Summary of INCB050465 Treatment-Related Serious Adverse Events During QW Schedule by MedDRA System Organ Class and Preferred Term	Safety	X	X
3.2.24	Summary of Treatment-Emergent Adverse Events Leading to INCB050465 Dose Reduction During QW Schedule by MedDRA System Organ Class and Preferred Term	Safety	X	
3.2.25	Summary of Treatment-Emergent Adverse Events Leading to INCB050465 Dose Interruption During QW Schedule by MedDRA System Organ Class and Preferred Term	Safety	X	
3.2.26	Summary of Treatment-Emergent Adverse Events Leading to Discontinuation of INCB050465 During QW Schedule by MedDRA System Organ Class and Preferred Term	Safety	X	X
3.3.1	Summary of Laboratory Values - Hematology	Safety	Safety X	
3.3.2	Shift Summary of Hematology Laboratory Values in CTC Grade - To the Worst Abnormal Value	Safety	X	X
3.3.5	Summary of Laboratory Values - Chemistry	Safety	Safety X	
3.3.6	Shift Summary of Chemistry Laboratory Values in CTC Grade - To the Worst Abnormal Value	Safety	X	X
3.4.1	Summary of Systolic Blood Pressure	Safety	X	
3.4.2	Summary of Diastolic Blood Pressure	Safety	Safety X	
3.4.3	Summary of Pulse	Safety	X	
3.4.4	Summary of Respiration Rate	Safety	X	
3.4.5	Summary of Body Temperature	Safety	X	
3.4.6	Summary of Weight	Safety	X	
3.5.1	Summary of PR Interval (msec) From 12-Lead ECG	Safety	X	
3.5.2	Summary of RR Interval (msec) From 12-Lead ECG	Safety	X	
3.5.3	Summary of QT Interval (msec) From 12-Lead ECG	Safety	X	
3.5.4	Summary of QRS Interval (msec) From 12-Lead ECG	Safety	X	
3.5.5	Summary of QTcF Interval (msec) From 12-Lead ECG	Safety	X	
3.5.6	Summary of Outliers of QT and QTcF Interval Values From 12-Lead ECG	Safety	X	X

Figures

Figure No.	Title	
4.1.1	Forest Plot of Overall Response Rate as Determined by IRC (Group A only)	
4.2.1	Kaplan-Meier Estimates of Duration of Response as Determined by IRC	
4.2.2	Kaplan-Meier Estimates of Duration of Response as Reported by Investigator (Group A only)	
4.2.3	Kaplan-Meier Estimates of Progression-Free Survival as Determined by IRC	
4.2.4	Kaplan-Meier Estimates of Progression-Free Survival as Reported by Investigator (Group A only)	
4.2.5	Kaplan-Meier Estimates of Overall Survival	
4.2.6	Waterfall Plot of Best Percentage Change in Sum of Target Lesions as Determined by IRC	
4.6	Line Graph of Mean Values Over Time for Selected Laboratory Values (Hemoglobin, Platelet Counts, WBC, Neutrophils, and Lymphocytes)	

Listings

Listing No.	Title
2.1.1	Subject Enrollment and Disposition Status
2.1.2	Subject Inclusion and Exclusion Criteria Violations
2.2	Protocol Deviations
2.3	Analysis Population
2.4.1	Demographic and Baseline Disease Characteristics
2.4.2	Disease History
2.4.3	Prior Systemic Therapy
2.4.4	Prior Surgery or Surgical Procedure
2.4.5	Prior Stem Cell Transplant
2.4.6	Medical History
2.4.7	Prior and Concomitant Medication
2.5.1	Study Drug Compliance
2.6.1	Best Overall Response, Duration of Response, and Progression-Free Survival per IRC
2.6.2	Best Overall Response, Duration of Response, and Progression-Free Survival per Investigator (Group A only)
2.6.3	Overall Response Assessment by Visit per IRC
2.6.4	IRC Response Assessment: Target Lesions
2.6.5	IRC Response Assessment: Non-target Lesions
2.6.6	IRC Response Assessment: New Lesions
2.6.7	Overall Response Assessment by Visit per Investigator
2.6.8	Investigator Response Assessment: Target Lesions
2.6.9	Investigator Response Assessment: Non-target Lesions
2.6.10	Investigator Response Assessment: New Lesions
2.6.11	Deaths and Overall Survival
2.7.1	Study Drug Administration
2.7.2	Adverse Events
2.7.3	Serious Adverse Events
2.7.4	Grade 3 and 4 Adverse Events
2.7.5	Fatal Adverse Events
2.7.6	Treatment-Related Adverse Events
2.7.7	Adverse Events Leading to Interruption, Reduction or Discontinuation of INCB050465

Listing No.	Title
2.8.1	Clinical Laboratory Values - Hematology
2.8.2	Clinical Laboratory Values - Chemistry
2.8.3	Abnormal Clinical Laboratory Values - Hematology
2.8.4	Abnormal Clinical Laboratory Values - Chemistry
2.9.1	Vital Signs
2.9.2	Abnormal Vital Sign Values
2.9.3	Alert Vital Sign Values
2.10.1	12-Lead ECG Values
2.10.2	Abnormal 12-Lead ECG Values
2.10.3	Alert 12-Lead ECG Values

Signature Manifest

Document Number: IC-STS-SAP-0115 **Revision:** 0

Title: INCB 50465-202 Statistical Analysis Plan

All dates and times are in Eastern Standard Time.

50465-202 SAP

Approval and Release

Name/Signature	Title	Date	Meaning/Reason
		22 Mar 2018, 05:17:42 PM	Approved
		22 Mar 2018, 09:01:08 PM	Approved
		23 Mar 2018, 01:12:28 PM	Approved
